7.1.4 FOLLOW-UP

A follow-up call (or visit, if deemed necessary by the Investigator) will be performed 7 to 10 days after the last intake of the study propellant for a safety follow-up.

The following assessments will be performed during this call/visit:

- AE recording: the status of any AEs ongoing at V7 (or the early termination visit) will be checked and updated in the eCRF, along with the related concomitant medications. Any new AE occurring since the last visit will be checked and recorded in the eCRF, as well as the related concomitant medications;

Clinical Study Code No.: CLI-05993AB6-06	Version No.: 1.0	Date: 16 February 2023
EudraCT number: 2022-003247-97		

- Concomitant medications: concomitant medications taken by the subject since V7 (or the early termination visit) will be checked and recorded.

7.2 STUDY ASSESSMENTS AND PROCEDURES

7.2.1 MUCOCILIARY CLEARANCE ASSESSMENT

Image acquisitions for MCC assessments, the transmission scan and the background scan will be performed at the timepoints specified in [Table 2](#).

On Day -1 of TP1 (before the assessment of MCC), the gamma scintigraphy procedure will be performed and will consist of a single transmission scan of the thorax, performed using a planar Co-57 source. The procedure will provide an outline of the lungs for use in subsequent analysis. A single background scan will also be performed during this visit, to account for background radiation. Subjects will be standing in front of the camera and any radioactive substance (except the markers) will be removed from the room.

On each visit with MCC assessments (see [Table 2](#)), subjects will be administered 99mTc-albumin colloid via a standardised aerosol delivery procedure. Controlled breathing conditions will be implemented using a metronome and commercial visual flow signal. A Mini 900 Ratemeter will be used to target a dose of 1-2 MBq (maximal dose of 2 MBq per administration). To assure that this adequate dose is achieved, the probe will be shielded with approximately 1 mm lead and will be taken from the middle of a subject's back. Inhalation time will vary by subject size and deposition efficiency, but is expected to be around 2 minutes per subject.

Gamma scintigraphy imaging will be performed over 240 minutes. Image acquisition will begin after completing the 99mTc-albumin administration, and the analysis of these images will provide a measurement of MCC. Anterior and posterior images of a 2-minute duration will be taken at 0 (immediately), 15 minutes, 30 minutes, 1 hour, 1 hour 30 minutes, 2 hours, 2 hours 30 minutes, 3 hours and 4 hours after the administration of the radiotracer. In order to allow accurate alignment of sequential images, an external anatomical marker containing a maximum of 0.02 MBq 99mTc will be taped to the subjects' chest and back, for the duration of the imaging procedures.

On Day 8 of each treatment period, the radiotracer will be administered post-dose, approximately 2 hours after administration of the last dose of the propellant.

Images will be reviewed and counts in each region of interest will be captured and corrected for background and radiation decay. To assess central *versus* peripheral deposition, the lung will be divided into central and peripheral (the area outside central) regions.

The procedure for the image acquisition and the measurement of MCC will be described in the laboratory manual.

The following parameters will be collected from the MCC measurements at each timepoint specified in [Table 2](#):

- PPR in whole lung;
- PPR in central lung region;
- PPR in peripheral lung region;
- Central/peripheral ratio.

The final data reporting will include the baseline measurements and measurements taken following each treatment period.

Clinical Study Code No.: CLI-05993AB6-06	Version No.: 1.0	Date: 16 February 2023
EudraCT number: 2022-003247-97		

The acquisition of the emission scans should start within the following time deviations from the end of the radiotracer inhalation:

- 0 (immediately) after: + 2 minutes;
- 15 minutes, 30 minutes, 1 hour, 1 hour 30 minutes, 2 hours, 2 hours 30 minutes, 3 hours and 4 hours after: \pm 5 minutes.

Longer time deviations will be evaluated on a case-by-case basis during the Data Review meeting.

7.2.2 LUNG FUNCTION ASSESSMENT

The lung function measurements will be assessed locally at the timepoints specified in [Table 2](#).

Lung function measurements will be performed according to the recommendations of the Official Statement of the European Respiratory Society and American Thoracic Society [25]. Subjects should be resting for at least 10 minutes before the lung function measurements and, during the measurement, they should be in sitting position with their nose clipped. Values will be corrected for body temperature, ambient pressure, gas saturated with water vapor conditions. Calibration of the spirometer must be performed by the same Investigator or designee (to the extent possible) and the reports must be kept with the study source documents.

The following parameters will be recorded:

- FEV₁ (L);
- FVC (L);
- Predicted FEV₁;
- FEV₁ percentage of predicted normal value;
- FEV₁/FVC ratio.

Predicted values of FEV₁ will be calculated according to formulas reported by Quanjer et al. [26].

For FEV₁ and FVC, the highest value from three technically satisfactory attempts will be recorded in the eCRF (irrespective of the curve they are derived from). The chosen value should not exceed the next one by more than 150 mL. If the difference is larger, additional (up-to 8) measurements will be made and the largest value will be reported. In order to be considered as technically satisfactory attempts, measurements should be free from cough and false-starts. FEV₁/FVC should be calculated from the highest FEV₁ and FVC values (even if the values do not come from the same curve).

In case abnormal lung function measurements were obtained at screening, (see inclusion criterion #9 in [Section 4.2](#) for details), the subject will be asked to return to the clinic once before randomisation to repeat the test. If, at that time, FEV₁/FVC > 0.70 and FEV₁ \geq 80% predicted, the subject can be included in the study. Otherwise, the subject will be discharged and recorded as a screening failure.

The spirometer used at the site will provide FEV₁/FVC values as a ratio. For eligibility purposes, values will be considered as acceptable if FEV₁/FVC is > 0.70.

The restrictions to be applied before spirometry assessments are described in [Section 4.4](#).

Assessments on Day 1 and Day 8 of TP1 and TP2 should be performed at the following timepoints:

- Pre-dose: within 30 minutes before the intake of the first inhalation of the propellant;
- Post-dose: 20 minutes after the intake of the last inhalation of the propellant.

Acceptable time deviations from theoretical post-dose timepoints are (actual time to be recorded is the time when the first lung function manoeuvre starts):

- 20 minutes post-dose (last inhalation): \pm 5 minutes.

Longer time deviations will be evaluated on a case-by-case basis during the Data Review meeting.

Clinical Study Code No.: CLI-05993AB6-06	Version No.: 1.0	Date: 16 February 2023
EudraCT number: 2022-003247-97		

7.2.3 VITAL SIGNS

Vital signs (SBP, DBP and SpO₂) and body temperature will be assessed at the timepoints specified in [Table 2](#).

Before the vital signs assessments, subjects should be resting in a quiet, supervised setting with minimal stimulation (e.g. no television, loud music, computer games) and, whenever possible, should lay in a supine position for 5 minutes before each assessment. Vital signs will be assessed either before or after the ECG recordings, and must be assessed before the lung function assessments and the blood tests, as specified in [Table 2](#).

At screening, SBP and DBP will be measured in duplicate (made within a 5-minute interval), and the average of the duplicate values will be used to assess subject eligibility, according to inclusion criterion #7 (see [Section 4.2](#)). In case abnormal blood pressure results are obtained at screening, the subject will be asked to return to the clinic once before randomisation, to repeat the blood pressure assessment. If, at that time, the averages of the duplicate parameters are within the allowed ranges, the subject can be included in the study. Otherwise, the subject will be discharged and recorded as a screening failure.

The vital signs assessments planned during the Investigational Phase (Day 1 and Day 8 of TP1 and TP2) and the early termination visit (in case of early termination) are duplicate SBP, DBP and single SpO₂.

Assessments on Day 1 and Day 8 of TP1 and TP2 should be performed at the following time points:

- Pre-dose: within 1 hour before the intake of the first inhalation of the propellant;
- Post-dose: 5 minutes, 15 minutes, and 1 hour 45 minutes after the intake of the last inhalation of the propellant.

Acceptable time deviations from theoretical post-dose timepoints are:

- 5 minutes and 15 minutes post-dose (last inhalation): ± 5 minutes;
- 1 hour 45 minutes post-dose (last inhalation): ± 15 minutes.

Tympanic body temperature will be measured at the timepoints specified in [Table 2](#). Results obtained at screening will be used to check the subjects' eligibility (see [Section 4.2](#), inclusion criterion #7).

Vital signs (SpO₂, SBP and DBP [single values and the average of duplicate measurements, as applicable]) and body temperature values will be reported in the eCRF.

7.2.4 ELECTROCARDIOGRAM ASSESSMENTS

ECG assessments will be performed at the timepoints specified in [Table 2](#).

Subjects should be resting in a quiet, supervised setting with minimal stimulation (e.g. no television, loud music, computer games) and, whenever possible, should lay in a supine position for 5 minutes before each assessment. ECG recordings will be performed either before or after the assessment of vital signs, and must be performed before the lung function assessments and the blood tests, as specified in [Table 2](#).

At screening, a triplicate 12-lead digitised ECG recording will be performed. The average of the triplicate recordings will be used to assess the subjects' eligibility (see exclusion criterion #8 in [Section 4.2](#)). In case abnormal ECG results are obtained at screening, the subject will be asked to return to the investigational site once before randomisation to repeat the ECG measurement. If, at that time, the averages of the triplicate ECG parameters are within the allowed ranges, the subject can be included in the study. Otherwise, the subject will be discharged and recorded as a screening failure.

Clinical Study Code No.: CLI-05993AB6-06

Version No.: 1.0

Date: 16 February 2023

EudraCT number: 2022-003247-97

The ECG assessments planned during the Investigational Phase (Day 1 and Day 8 of TP1 and TP2) and the early termination visit will consist in single ECGs, and will be performed for safety assessments.

ECG assessments on Day 1 and Day 8 of TP1 and TP2 should be performed at the following time points:

- Pre-dose: within 1 hour before the intake of the first inhalation of the propellant;
- Post-dose: 5 minutes, 15 minutes and 1 hour 45 minutes after the intake of the last inhalation of the propellant.

Acceptable time deviations from theoretical post-dose timepoints are:

- 5 minutes and 15 minutes post-dose (last inhalation): ± 5 minutes;
- 1 hour 45 minutes post-dose (last inhalation): ± 15 minutes.

The values of all ECG parameters and the overall ECG evaluation will be reported in the eCRF.

7.2.5 BLOOD SAMPLE COLLECTION FOR SAFETY EVALUATION

Subjects should be fasting for at least 10 hours before the blood samples are collected (see [Section 4.4](#)). Moreover, blood sample collection should be done after the ECG and blood pressure assessments (before the subject is discharged from the clinic).

At screening, blood sample collections and blood safety evaluations will be performed as follow:

- 5 mL of blood will be collected for clinical chemistry testing (creatinine, urea, aspartate aminotransferase [AST], alanine aminotransferase [ALT], gamma-glutamyl transpeptidase [γ -GT], total bilirubin, alkaline phosphatase, sodium, potassium, albumin);
- 4 mL of blood will be collected for haematology testing (red blood cell [RBC] count, white blood cell [WBC] count and differential, total haemoglobin [Hb], haematocrit [Hct], platelets [PLT] count);
- 5 mL of blood will be collected for:
 - Serology testing (HIV1, HIV2, hepatitis B and hepatitis C);
 - Serum pregnancy test and FSH test.

Note: For logistical reasons, both the pregnancy test and FSH test will be performed by the local laboratory for blood samples collected from all female subjects. However, only the relevant results will be recorded in the eCRF (i. e. pregnancy tests for WOCBP and FSH tests for post-menopausal women).

- 2 mL of blood will be collected for the assessment of fasting glucose.

In case abnormal laboratory values are obtained at screening that could indicate a temporary condition (see exclusion criterion #3 in [Section 4.3](#) for details), the subject will be asked to return to the clinic once before randomisation, to repeat the test. If, at that time, no abnormalities are observed, the subject can be included in the study, otherwise the subject will be discharged and recorded as a screening failure.

Clinical Study Code No.: CLI-05993AB6-06	Version No.: 1.0	Date: 16 February 2023
EudraCT number: 2022-003247-97		

On Day 8 of TP2, or during the early termination visit (in case of early termination), blood samples will be collected and blood safety evaluations will be performed as follow:

- 5 mL of blood for clinical chemistry testing (creatinine, urea, AST, ALT, γ -GT, total bilirubin, alkaline phosphatase, albumin, sodium, potassium);
- 4 mL of blood for haematology testing (RBC count, WBC count and differential, total Hb, Hct, PLT count);
- 2 mL of blood for fasting glucose.

Blood collection and sample preparation will be performed according to procedures provided by the local laboratory which will be in charge of transmitting the results to the Investigator for entry in the eCRF.

7.2.6 URINE SAMPLE COLLECTION FOR SAFETY EVALUATION

A single urine sample of at least 20 mL will be collected at screening, and the following analyses will be performed:

- Dipstick urinalysis: bilirubin, urobilinogen, ketones, glucose, proteins, blood, nitrite, potential of hydrogen (pH), specific gravity, and leukocytes;
- Point of care drugs of abuse: methamphetamine, cocaine, cannabis, amphetamines, morphine/opiates, benzodiazepines, methylenedioxymethamphetamine, methadone, tramadol and ketamine;
- Point of care urine sample for cotinine.

A single urine sample of at least 20 mL will be collected on Day -1 and Day 8 of each treatment period (or the early termination visit, in case of early termination), and the following analyses will be performed:

- Point of care pregnancy test (except for Day 8 TP1);
Note: For logistical reasons, the urine pregnancy test will be performed for urine samples collected from all female subjects. However, only the relevant results (pregnancy tests for WOCBP) will be recorded in the eCRF.
- Point of care drugs of abuse: methamphetamine, cocaine, cannabis, amphetamines, morphine/opiates, benzodiazepines, methylenedioxymethamphetamine, methadone, tramadol and ketamine;
- Point of care urine sample for cotinine.
Note: In case of positive results for cotinine and drug tests at screening or prior to randomisation, the tests can be repeated once at Investigator's discretion.

Urine samples will be collected and prepared according to the instructions provided in the test kits. Results of these assessments will be entered in the eCRF by the Investigator or designee.

7.2.7 DAILY RECORD CARD

Subjects will be given a DRC at Day 1 of each treatment period and will be instructed on how to complete it. Subjects will also be asked to bring the completed DRC with them to the next visit at the investigational centre (i.e. Day 8 of that treatment period). In case a subject discontinues from the study during a treatment period, he/she will be asked to bring the DRC at the early termination visit.

As indicated in [Table 2](#), subjects will use the DRC (one for each treatment period) to record the intake of the study propellant (for the assessment of treatment compliance). Subjects will also record the use of any concomitant medication and the occurrence of any AE (for the assessment of treatment safety).

Clinical Study Code No.: CLI-05993AB6-06

Version No.: 1.0

Date: 16 February 2023

EudraCT number: 2022-003247-97

Data collected throughout the DRC will be entered in the eCRF, as described in [Section 11](#).

8. STUDY ASSESSMENTS

The **primary objective** of this study is to assess the effect of multiple doses of the HFA-152a propellant and the HFA-134a propellant (when administered not in combination with active compounds) on MCC.

The MCC assessment will be performed on Day -1 and on Day 8 of each treatment period, as described in [Section 7.2.1](#).

The following **study variables** will be considered to **assess the primary objective** of the study:

- MCC rate, as assessed by the percent particle retention at 2 hours after the inhalation of radiolabelled particles (PPR₂);
- MCC rate, as assessed by the percent particle retention at 4 hours after the inhalation of radiolabelled particles (PPR₄).

Note: PPR in whole lung will be used for the assessment of the variables above.

The following **study variable** will **complete the evaluation of the primary objective** of the study:

- MCC, as assessed by the area under the tracheobronchial particle retention curve between 0 and 4 hours (AUC₀₋₄) after the inhalation of radiolabelled particles.

9. SAFETY ASSESSMENTS

The **secondary objective** of the study is to evaluate the general safety and tolerability of the two different propellants.

The general safety and tolerability of the propellants will be assessed during each treatment period, by local safety ECGs (as described in [Section 7.2.4](#)), vital signs (as described in [Section 7.2.3](#)), lung function assessment (as described in [Section 7.2.2](#)) and collection of AEs. Moreover, subjects will use DRCs to report AEs and the use of concomitant medications during the treatment periods (as described in [Section 7.2.7](#)).

The following **safety variables** will be considered for the evaluation of the general safety and tolerability of each propellant:

- AEs;
- Vital signs (SBP, DBP and SpO₂);
- 12-lead ECG parameters: HR, QTcF, PR and QRS;
- Lung function parameters: FEV₁ and FVC.

10. ADVERSE EVENT REPORTING

10.1 DEFINITIONS

An **Adverse Event (AE)** is any untoward medical occurrence in a subject to whom a medicinal product is administered and which does not necessarily have a causal relationship with this treatment.

An AE can therefore be any unfavourable and unintended sign (including an abnormal laboratory finding), symptom, or disease temporally associated with the use of a medicinal product, whether or not considered related to the medicinal product.

An **Adverse Drug Reaction (ADR)** is a noxious and unintended response to an IMP related to any dose administered.

Clinical Study Code No.: CLI-05993AB6-06

Version No.: 1.0

Date: 16 February 2023

EudraCT number: 2022-003247-97

Within this study, the causality of an AE has to be considered with regards to the placebo and its excipients.

All AEs judged by either the reporting Investigator or the Sponsor as having a reasonable causal relationship to a medicinal product qualify as adverse reactions.

Adverse reactions could derive from medication errors and uses outside what is foreseen in the protocol in relation to the IMP, including misuse and abuse of the product.

A **Serious Adverse Event (SAE)/Serious ADR** is any untoward medical occurrence or noxious and unintended response to an IMP that, at any dose, falls into one or more of the following categories:

- **Results in death**

Death is not an AE but an outcome. It is the cause of death that should be regarded as the AE. The only exception to this rule is “sudden death” where no cause has been established; in this instance, “sudden death” should be regarded as the AE and “fatal” as its reason for being serious.

- **Is life-threatening**

“Life-threatening” refers to an event in which the subject was at risk of death at the time of the event (e.g. aplastic anaemia, acute renal failure, anaphylaxis). The term does not refer to an event which hypothetically might have caused death if it were more severe.

- **Requires hospitalisation or prolongation of existing hospitalisation**

Hospitalisation refers to a situation whereby an AE is associated with unplanned formal overnight admission into hospital, usually for purpose of investigating and/or treating the AE. Hospitalisation for the treatment of a medical condition that occurs on an “elective” or “scheduled” basis or for a pre-existing condition that did not worsen during the study should not necessarily be regarded as an AE. Complications that occur during the hospitalisation are AEs. If a complication prolongs hospitalisation, the event is an SAE. Emergency room visits that do not result in a formal admission into hospital should be evaluated for one of the other seriousness criteria (e.g. life-threatening, persistent or significant disability or incapacity, medically significant).

- **Results in persistent or significant disability or incapacity**

The term “significant disability” should be viewed as any situation whereby an AE has a clinically important effect on the subject’s physical or psychological well-being to the extent that the subject is unable to function normally.

- **Is a congenital anomaly or birth defect**

- **Is a medically significant AE**

This criterion allows for any situation in which important AEs/adverse reactions that are not immediately life-threatening or do not result in death or hospitalisation may jeopardise the subject’s health or may require intervention to prevent one of the above outcomes.

Medical and scientific judgment should be exercised in deciding whether an event is “serious” in accordance with those criteria.

Examples of such events are intensive treatment in an emergency room or at home for allergic bronchospasm; blood dyscrasias or convulsions that do not result in hospitalisation; or development of drug dependency or drug abuse.

Any suspected transmission via a medicinal product of an infectious agent is also considered a serious adverse reaction.

Clinical Study Code No.: CLI-05993AB6-06

Version No.: 1.0

Date: 16 February 2023

EudraCT number: 2022-003247-97

A **Non-Serious AE/Non-Serious ADR** is an AE or ADR that does not meet the criteria listed above for an SAE/serious ADR.

10.2 EXPECTEDNESS

Since no active ingredient will be included in the study treatment but only pMDI containing placebo propellant and excipients will be administered, there is no reference document for the assessment of the expectedness of AEs in this study. All AEs assessed as related to the study treatments and/or their excipients will be considered as unexpected AEs for safety reporting purposes.

10.3 INTENSITY OF ADVERSE EVENT

Each AE must be rated on a 3-point scale of increasing intensity:

- **Mild:** the event causes a minor discomfort or does not interfere with daily activity of the subject or does not lead to either modification of test treatment dosage or establishment of a correcting treatment;
- **Moderate:** the event perturbs the usual activity of the subject and is of a sufficient severity to make the subject uncomfortable. The event leads to a diminution of dosage of the test treatment, or a temporary interruption of its administration or to the establishment of a correcting treatment;
- **Severe:** the event prevents any usual routine activity of the subject and causes severe discomfort. It may be of such severity to cause the definitive interruption of test treatment.

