5.2 NON-PERMITTED CONCOMITANT MEDICATIONS

1. From 3 months before screening and up-to the end of the follow-up period: any enzyme-inducing drugs, enzyme-inhibiting drugs, biologic drugs or any drug known to have a well-defined potential for hepatotoxicity (e.g. isoniazide, nimesulide, ketoconazole);
2. From 3 weeks before randomisation and up-to the end of the follow-up period: any drug treatment, including prescribed or over-the-counter medicines, vitamins, herbal medicines, homeopathic remedies, etc., with the exception of the allowed concomitant medications specified above.

Clinical Study Code No.: CLI-05993AB6-06

Version No.: 1.0

Date: 16 February 2023

EudraCT number: 2022-003247-97

The wash-out requirements prior to the assessments of MCC and lung function are summarised in [Section 4.4](#).

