6.1 TREATMENTS BEING INVESTIGATED

6.1.1 APPEARANCE AND CONTENT

Test treatment: placebo HFA-152a propellant pMDI, presented as:

- Active ingredients: none;
- Excipients: HFA-152a propellant, [REDACTED];
- Presentation: each canister contains 120 doses;
- Appearance: aluminium canister + grey actuator.

Reference treatment and training kit: placebo HFA-134a propellant pMDI*, presented as:

- Active ingredients: none;
- Excipients: HFA-134a propellant, [REDACTED];
- Presentation: each canister contains 120 doses;
- Appearance: aluminium canister + grey actuator.

*For this study, CHF 1535 placebo HFA-134a propellant pMDI will be used.

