10.4 CAUSALITY ASSESSMENT

In determining whether an AE is an ADR, consideration shall be given to whether there is a reasonable possibility of establishing a causal relationship between the event and the IMP (to be intended as both the tested product and the reference product), based on an analysis of available evidence.

The following “binary” decision choice will be used by the Investigator to describe the causality assessment:

Is there a reasonable possibility of relatedness to study drug?

- *Yes*
- *No*

The expression “reasonable possibility of relatedness” is meant to convey, in general, that there are facts (evidence) or arguments meant to suggest a causal relationship.

The Investigator will be asked to consider the following before reaching a decision on causality assessment:

- Time relationship between study drug intake and event’s onset;
- Dechallenge (did the event abate after stopping drug?);
- Rechallenge (did the event reappear after reintroduction?);
- Medical history;
- Study treatment(s);
- Mechanism of action of the study drug;
- Class effects;
- Other treatments (prior or concomitant);

Clinical Study Code No.: CLI-05993AB6-06

Version No.: 1.0

Date: 16 February 2023

EudraCT number: 2022-003247-97

- Withdrawal of study treatment(s);
- Worsening of existing condition;
- Erroneous treatment with study medication (or concomitant medication);
- Protocol-related process.

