12. STATISTICAL METHODS

12.1 SAMPLE SIZE

No formal sample size calculation has been performed for this study, considering its exploratory nature. A total of 20 subjects will be randomised in the study in order to reach at least 18 evaluable subjects.

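### The adverse event intensity scale lets one event meet both Mild and Severe, and its action clauses name only the test treatment

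*Protocol*

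**What the plan says.** Protocol 10.3 sets the rule: "Each AE must be rated on a 3-point scale of increasing intensity". The three grades are built differently.

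- **Mild** opens "the event causes a minor discomfort or does not interfere with daily activity of the subject or does not lead to". Its third alternative reads in full "or does not lead to either modification of test treatment dosage or establishment of a correcting treatment". The three parts are joined by 'or', so any one is enough.
- **Moderate** has two sentences. The first requires disturbed activity together with discomfort. The second says that the event leads to a lower dose of the test treatment, a temporary interruption of it, or a correcting treatment.
- **Severe** requires that routine activity is prevented and that discomfort is severe. Its treatment sentence is permissive: "It may be of such severity to cause the definitive interruption of test treatment".

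The term used in the action clauses is defined elsewhere. Protocol 6.1.1 has "Test treatment: placebo HFA-152a propellant pMDI, presented as", and HFA-134a is there called the reference treatment. Protocol 1.2, 3 and 6.1.2.2 and SAP 1.2 use the same pair of terms. Protocol 10.4, on causality, says that the IMP is "to be intended as both the tested product and the reference product". Protocol 10.5 speaks of the study drug. Protocol 10.3 has no such extension.

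Intensity is collected for every event (SAP 3.1.1). Severe events are reported by treatment (Protocol 12.3.5; SAP 3.1.3 and Table 14.3.1.7). Action taken is recorded separately under Protocol 10.5 and 10.6.

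**The concern.** An ordered scale should give each event exactly one grade. Here one route into Mild does not describe intensity at all: it describes what was done about the event. A severe event left untreated, with dosing continued, qualifies as Mild by that route while also meeting Severe.

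The study is open-label, so where two grades fit, the person choosing knows which propellant was given. The severe-event table belongs to the secondary objective, the safety and tolerability of the two propellants. A grading rule that leaves a choice, and that names one propellant in its action clauses, weakens consistency between graders and between periods.

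**Working it through.** The plan states no figure to reproduce. The check is to apply the wording of Protocol 10.3 to defined cases.

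**Case 1: overlap.** Routine activity prevented, severe discomfort, dosing unchanged, no correcting treatment.
- Severe: both required conditions hold. Interruption of treatment is optional.
- Mild: the third alternative holds.
- Result: Mild and Severe, on either propellant and however the term test treatment is read.

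**Case 2: the Moderate boundary.** Activity disturbed, subject uncomfortable, no action of any kind.
- Moderate: first sentence met, action sentence not met.
- Mild: third alternative met.
- Result: Mild, although the event fits Moderate's description of how it affects the subject.

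**Case 3: the defined term.** Activity disturbed, subject uncomfortable, no correcting treatment, temporary interruption of the period's treatment.
- HFA-152a period: the interruption is of the test treatment. Moderate is met and Mild is not.
- HFA-134a period, term read as defined: the test treatment is not modified. Mild is met and Moderate is not.
- If the term is read to cover both products, the two periods agree (Moderate).

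**Enumeration.** To see how far this goes, every combination of four attributes was graded: discomfort (minor, uncomfortable, severe), activity (unaffected, disturbed, prevented), correcting treatment (no, yes) and dose action (none, reduced, temporary stop, definitive stop). That gives 3 × 3 × 2 × 4 = 72 profiles. Each level was matched exactly to the words of the grade.

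| Grades met | HFA-152a, term as defined | HFA-134a, term as defined | Either propellant, term covering both |
|---|---|---|---|
| Mild only | 43 | 52 | 43 |
| Moderate only | 6 | 4 | 6 |
| Severe only | 7 | 4 | 7 |
| Mild and Severe | 1 | 4 | 1 |
| None | 15 | 8 | 15 |
| Total | 72 | 72 | 72 |

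With the term as defined, 12 of 72 profiles are graded differently by propellant. Going from HFA-152a to HFA-134a:
- 6 − 4 = 2 move from Moderate to Mild;
- 15 − 8 = 7 move from no grade to Mild;
- 7 − 4 = 3 stay Severe but acquire Mild as an alternative;
- 2 + 7 + 3 = 12.

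With the term covering both products, 0 differ.

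The number of profiles meeting Severe is the same for both: 7 + 1 = 8 on HFA-152a and 4 + 4 = 8 on HFA-134a.

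**Would 'and' repair Mild?** It removes the overlap (0 of 72 in both Mild and Severe). But 57 of 72 profiles then fit no grade with the term covering both products, and 5 of 72 still differ by propellant with the term as defined. Changing the connective alone is not a repair.

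These counts describe the logic of the wording. They are not event frequencies.

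**The case against.** The case for leaving the text alone has several parts.

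- **A sensible grader would choose Severe for a disabling event**, because the scale is said to run in increasing intensity. That supports the higher grade but does not require it. The worst-case rules in the SAP deal with incomplete event dates (3.1.2) and with parameters that have defined abnormalities (5.2.5), not with intensity.
- **The term test treatment is probably meant generically.** Sections 10.4 and 10.5 point that way, and nothing suggests that different grading was intended. This stands as a reading of intent, and makes that part a correction of terms. The overlap in Case 1 does not depend on it.
- **A misgraded event would be visible.** Intensity and action taken are collected per event and all events are listed (SAP 3.1.3 and Listing 16.2.7.2). This stands, and it limits the harm.

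Stronger readings are also tempting, and the documents do not support them.

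- A reader might infer that stopping treatment raises an event to Severe on HFA-152a only, so that the severe count is built unequally. Interruption is neither necessary nor sufficient for Severe, and the same 8 profiles' worth of cases meet it on each propellant. What remains is indirect: three more disabling profiles on HFA-134a also fit Mild, which matters only if a grader picks Mild for a disabling event.
- A reader might infer from the medication ban ("any drug treatment, including prescribed or over-the-counter medicines") that nearly all events will go without action and so be Mild. Section 5.1 permits some medicines, 10.5 allows interruption and withdrawal, and 10.6 allows specific therapy. No frequency can be derived.
- A reader might infer that a slight complaint treated with a permitted analgesic is both Mild and Moderate. Moderate first requires disturbed activity and discomfort, so such an event is Mild only.

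**Conclusion.** The rule is defective as written, and the defect is minor. One clear type of event, disabling and severely uncomfortable with dosing unchanged and no correcting treatment, meets two grades with no rule to decide between them. Events of moderate effect that prompt no action fall to Mild. Read literally, the action clauses also shift some events between Moderate and Mild according to propellant; that part rests on applying the protocol's own definition of test treatment.

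The size in practice cannot be estimated from the documents. If all 20 planned subjects receive both propellants, one subject added to or removed from the severe category moves that propellant's percentage by 1/20 = 5 points. That is true of any single reclassification and says nothing about how likely one is. The severe table is descriptive, with no test attached, and the clearance endpoints are unaffected.

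**What to change.** Reword Protocol 10.3 in one of two ways.

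1. **Preferred:** define the three grades on discomfort and interference with activity only, so that they exclude one another, and drop the dosage and correcting-treatment clauses. Nothing is lost, since 10.5 and 10.6 already record the action. The two attributes give 3 × 3 = 9 combinations, of which only 3 agree in level, so the text should also say how the other 6 are graded, for example by the worse of the two.
2. **Minimum:** keep the present text and add that the highest grade whose activity and discomfort criteria are met is assigned. This settles Cases 1 and 2.

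Wherever an action clause is kept, replace test treatment with study treatment (HFA-152a or HFA-134a). This settles Case 3.

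The cost is protocol wording and matching eCRF completion guidance, with no new data item, table or analysis. If events have already been graded, the study report should state the convention that was used.
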